7.2 Study enrolment

7.2.1 Selection of patients for recruitment and enrolment

At each site, patients (or parents/guardians on behalf of minors) will be invited to participate in the study when they present with fever to the participating health facilities for care.

Health centre staff will work with study staff to identify patients who present with fever.

Study staff will screen and enrol participants according to the selection criteria listed in section 6. A total of 2400 patients will be enrolled at each site (see sample size calculations in section 11.3), with approximately half being outpatients and half inpatients. If a patient is enrolled as an outpatient but deteriorates clinically and is admitted to hospital within <24 hours after enrolment, the patient will be re-classified as an inpatient for study purposes. If a patient is enrolled as an outpatient and then admitted ≥ 24 hours after enrolment, s/he will remain listed as an outpatient for study data purposes.

Since the causes of fever are likely to be different in children and adults, enrolment will be stratified so that participants are enrolled in two age groups of approximately equal numbers: children aged two months (≥ 2 months) to <15 years, and those aged 15 years and older. In addition, so that results accurately represent the patient population at each site, site-specific recruitment strategies will be developed to achieve enrolment of a random sample of patients presenting throughout the day and week (including those presenting after hours or at weekends, who may come from areas further from the health facility, and/or have more severe presenting symptoms) and over the course of the 12-month

recruitment period. In each of the four categories defined by age and in-/outpatient status, 12 consecutive patients per week will be recruited. The day of the week that recruitment starts will be rotated. There may be slight variations on this strategy due to site specific constraints. The total number of patients presenting to the hospital with fever each day (or week), including those not in the study, over the course of the study period will be recorded.

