In addition, questionnaires will be administered to the community control participants in order to capture more representative data about treatment seeking and medicine (primarily antimicrobial) use. To increase the statistical power of this health care utilisation survey, as for other recent studies that estimate incidence and “burden” of infections,^{21,34} for each control participant, the participant (or head of household or health care decision-maker if the participant is a child) also will be asked about basic demographic information (date of birth or age, and gender) and treatment seeking practices for each household member. This health care utilisation survey will provide an estimate of the period prevalence of fever as well as the proportion of persons with fever in the community who present to the study enrolment sites for care. The fraction of persons with fever presenting to a study site will be used to calculate multipliers to estimate the population-based incidence of fever overall, and the incidence of specific causes of fever in the catchment area of study health care

facilities. This “multiplier” method is well established^{1,22} and is widely used for estimating the incidence of febrile illnesses including but not limited to brucellosis,³⁵ leptospirosis,²¹ and typhoid fever.³⁶ The multiplier method requires an estimate of the total number of cases of fever that present to our study sites. The multiplier method also requires an estimate of the proportion of cases of fever in the population who do not present to the study hospital, which will be obtained through the healthcare utilisation survey among controls. It will also require an estimate of the catchment population for each site, or if that is not possible, for a defined population around each site (which may be smaller than the total catchment area). In the latter case, only health care utilisation data from controls and their household members in the defined population will be used for the estimate of the population incidence of fever in the defined population.

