11.1 Quantitative outcome measures and analysis

Listed by study objective:

- 1) To determine the treatable and/or preventable causes of fever in children and adults presenting as outpatients, and among those admitted to hospitals, in areas represented by the study sites;

For outpatients the attributable fraction (AF) will be calculated for each pathogen or group of pathogens. This will be done separately for each site and age stratum. For each group of patients, the odds ratio (OR) for the association between each pathogen and fever will be calculated by comparing cases and controls. Logistic regression will be used to calculate the odds ratio. In order to take the matched design into account, strata based on geographical location and season will be defined at each site and the analysis will be adjusted for age, sex and stratum. Since cases and controls are recruited at a constant rate throughout the year but fever incidence is likely to vary by season, the analysis will be weighted by the proportion of patients included in the study of the total number of cases seen at the study

site in the given season. AF will then be calculated as $AF_A = p_A(1-OR_A)$. Confidence intervals will be calculated in an appropriate way, e.g. bootstrapping or delta method.

For inpatients, first the distribution of diagnoses in each site will be tabulated for all inpatients in the study. Then a second analysis to calculate AFs will be carried out for inpatients, but this will be restricted to inpatients who come from the same geographical area as the controls. The calculation of AFs for inpatients may be dropped if insufficient numbers of in-patients come from the same area as the controls.

- 2) To determine how fever aetiology varies according to patient age, level of the health system, geographical area, local malaria and HIV prevalence, and other risk factors;

Stratified analyses will be carried out as above to estimate the AF for sub-groups of patients.

- 3) To determine the prevalence and spectrum of antimicrobial resistance among bacterial pathogens identified in clinical specimens from febrile patients;

At each site the proportion of bacterial pathogens with antimicrobial resistance defined by standardized criteria will be calculated. The proportion of common organisms demonstrating resistance to a standard panel of antibiotics will be reported.

Specific secondary objectives:

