1) To generate data on incidence of specific infections among study participants, and therefore contribute key data on disease burden for some infections that are not counted in current “global burden of disease” estimates;

For an area whose population size is known, a health utilization survey will be used to estimate r , the proportion of fevers for which treatment was sought at a study centre. The total number of cases seen at the study site from the defined population will be multiplied by $1/r$, to obtain the total cases in a year from the defined population. This will be divided by the size of the population to estimate incidence. Incidence of fever caused by specific pathogens will be calculated by multiplying the incidence by the AF for that pathogen.

3) Evaluation of available biomarker assays to assess their performance and potential utility in fever case management in the study areas;

The sensitivity, specificity, and positive and negative predictive value of each biomarker will be estimated.

4) To generate data to support the development of new fever case management algorithms which may be evaluated in future studies;

The association between the presence of pathogens with predefined clinical and other variables will be examined.

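### Pathogen-specific incidence rests on one all-fever care-seeking proportion and an unspecified attributable fraction, so it can be biased when causes differ between in- and outpatients

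*Protocol*

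**What the plan says.** Protocol section 11.1, under secondary objective 1, writes the estimator out. The health utilisation survey supplies r, "the proportion of fevers for which treatment was sought at a study centre". Then "The total number of cases seen at the study site from the defined population will be multiplied by $1/r", and division by the population size gives fever incidence. Finally, "Incidence of fever caused by specific pathogens will be calculated by multiplying the incidence by the AF for that pathogen".

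Section 7.5.4 describes the same method: "The fraction of persons with fever presenting to a study site will be used to calculate multipliers". The plural is used, but no strata are named.

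On the AFs, section 11.1 (primary objective 1) plans outpatient AFs: "This will be done separately for each site and age stratum". For inpatients it plans a table of diagnoses and a second AF analysis limited to those from the controls' area, with an exit: "The calculation of AFs for inpatients may be dropped if insufficient numbers of in-patients come from the same area as the controls". The only weighting described is by season.

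Section 7.2.1 enrols 2400 patients per site, "with approximately half being outpatients and half inpatients", whereas section 3.2 notes that most febrile attenders are not admitted. Section 7.2.1 also has the total number of febrile attenders recorded, without stating a split by admission.

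**The concern.** The study keeps in- and outpatients apart in enrolment and in estimating AFs, but the incidence formula merges them: one case count, one r, one AF. Two things are left open that affect the answer.

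First, the formula does not say which AF is meant. If the outpatient AF is applied to a count that includes inpatients, the inpatient causes drop out. This needs no assumption about care-seeking, only that causes differ by level of care.

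Second, if admitted fevers reach the study site more often than other fevers, a single 1/r scales the admitted cases up too far, even with an AF that reflects the real mix of attenders.

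Secondary objective 1 is meant to supply burden figures for infections missing from current estimates. Infections that mainly lead to admission are the ones most exposed to this error.

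**Working it through.** The protocol gives no value for r, for any AF or for incidence, so there is no stated figure to reproduce. The formula is compared with its stratified counterpart.

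**Notation.** N_out and N_in are febrile attenders per year from the defined population. r_out is the share of non-admitted community fevers seen at the site; r_in is the share of admitted fevers that were admitted at the site. AF_out and AF_in are the pathogen's attributable fractions.

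- Community fevers: F = N_out/r_out + N_in/r_in
- Overall proportion: r = (N_out + N_in)/F
- As written: cases = (N_out + N_in)/r × AF = F × AF
- Stratified: cases = (N_out/r_out) × AF_out + (N_in/r_in) × AF_in

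Since (N_out + N_in)/r = F, total fever incidence is correct with a single r. Only the cause-specific step can go wrong.

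**Assumed inputs (none from the protocol).** N_out = 9000, N_in = 1000; r_out = 0.20; r_in = 0.4, 0.7 or 0.9; AF_out = 0.5%, AF_in = 8%. The AF weighted to the attender mix is (9000 × 0.005 + 1000 × 0.08)/10,000 = 125/10,000 = 1.25%.

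**Worked case, r_in = 0.7.** F = 9000/0.20 + 1000/0.7 = 45,000 + 1,429 = 46,429, and r = 10,000/46,429 = 0.215. Stratified cases = 45,000 × 0.005 + 1,429 × 0.08 = 225 + 114 = 339. As written with AF_out: 46,429 × 0.005 = 232, ratio 0.68. As written with the weighted AF: 46,429 × 0.0125 = 580, ratio 1.71.

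| | r_in 0.4 | r_in 0.7 | r_in 0.9 |
|---|---|---|---|
| Community fevers F | 47,500 | 46,429 | 46,111 |
| Overall r | 0.211 | 0.215 | 0.217 |
| Stratified cases | 425 | 339 | 314 |
| As written, outpatient AF | 238 | 232 | 231 |
| Ratio to stratified | 0.56 | 0.68 | 0.73 |
| As written, weighted AF | 594 | 580 | 576 |
| Ratio to stratified | 1.40 | 1.71 | 1.84 |

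**Equal care-seeking, r_in = r_out = 0.20.** F = 50,000; stratified cases = 45,000 × 0.005 + 5,000 × 0.08 = 625. The weighted AF gives 50,000 × 0.0125 = 625, ratio 1.00, so that error disappears. The outpatient AF gives 250, ratio 0.40, so that one does not.

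**Milder contrast, AFs of 1% and 4%.** The weighted AF is (90 + 40)/10,000 = 1.3%. At r_in = 0.4: 47,500 × 0.013 = 617.5 against 450 + 100 = 550, ratio 1.12. At r_in = 0.9: 46,111 × 0.013 = 599 against 450 + 44 = 494, ratio 1.21. The error shrinks as the causes become more alike.

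**The case against.** Four arguments can be made for the plan.

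*The AFs are not lumped together.* A reader might infer that the protocol uses one AF for all fevers. It does not: section 11.1 estimates AFs by site and age for outpatients, treats inpatients separately, and adds subgroup AFs under primary objective 2, whose wording there includes level of the health system. This stands. The gap is that the incidence step does not say which of these AFs is used or how they combine.

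*Inflation is not established.* A reader might also infer that severe infections will be overstated. Section 7.5.1 links the outpatient-matched controls to precision for secondary objective 1, which suggests the outpatient AF, and that AF gives understatement. A reader might go further and pool AFs over the roughly 1:1 enrolled sample. Under the assumptions above that AF is (0.5% + 8%)/2 = 4.25%, which gives 4.8 to 6.2 times the stratified value. No section plans this pooling, so those figures are hypothetical.

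*Care-seeking by severity is unknown.* The documents give no figures. Health posts in Mozambique and primary care clinics in Zimbabwe are study facilities (section 7.1.1), which may raise r for mild fever, and patients beyond a site's capacity are referred on (section 7.3.3). The gap may be small at some sites. Nor does section 3.2 say that severe disease has other causes; it describes the inpatient goal as similar to the outpatient one. This stands, and the sizes above are illustrations.

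*Detail may be left to an analysis plan.* Stratifying the multipliers could be, and the plural in section 7.5.4 leaves room for it. But section 11.1 does not leave the formula open: it defines r over all fevers and applies it to all cases. Splitting it later also depends on data collected in the field.

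**Conclusion.** The point holds for pathogen-specific incidence only; total fever incidence is not biased by a single r. Followed as written, the formula misstates the incidence of a pathogen whose frequency differs between in- and outpatients, and the direction depends on an AF that the text does not name. With the firmly planned outpatient AF, an infection that mainly leads to admission is understated whether or not care-seeking differs. With an AF weighted to the attender mix it is overstated, but only if admitted fevers reach the site more often than others.

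The sizes depend on the assumed volumes, care-seeking proportions and pathogen frequencies, and they fall towards 1 as in- and outpatient causes converge. The documents do not support a general claim that severe infections will be inflated, or that severe fevers attend far more often. Since the objective is secondary and the repair is cheap, the formula should be changed, but the primary objectives are not affected.

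**What to change.** In section 11.1, replace the incidence formula with a sum over level of care, computed within age group:

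[(N_out/r_out) × AF_out + (N_in/r_in) × AF_in] / population

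- If the inpatient AF is dropped, use the inpatient diagnosis frequency in its place and say that it does not subtract background prevalence.
- Count N_out and N_in separately among febrile attenders from the defined population, applying the 24-hour reclassification rule of section 7.2.1 to both.
- Make sure the utilisation survey records, for each fever episode, whether the person was admitted and where. The questionnaire is not shown and may already do so.
- If the survey finds too few admitted fevers to estimate r_in at a site, report the incidence of inpatient diagnoses as an unscaled minimum, labelled as such, with a sensitivity range for r_in.
- State as a limitation that, within each stratum, fevers that never reach the site are assumed to share the causes of those that do. The stratified sum does not remove this assumption.

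The cost is a revised formula, a split in a count already being kept, and at most one survey item. The price in precision is a wider interval for the inpatient component, because few surveyed fevers will have led to admission.

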6 STUDY POPULATION AND SELECTION CRITERIA

Participants will be patients who present with fever for health care at the selected health care facilities. Patients of all ages two months and older will be eligible for enrolment. Study sites include outpatient and inpatient facilities in Laos, Malawi, Mozambique, Myanmar, and Zimbabwe. Patients will be recruited if they fulfil all of the following criteria (see also section 7.2 on participant enrolment, and Screening and Enrolment Forms [Appendix C]):

- 1) Tympanic or axillary temperature $\geq 37.5^{\circ}\text{C}$ at presentation;
- 2) Not having been hospitalized or having undergone surgery in the previous month;
- 3) Age ≥ 2 months (two months or older);
- 4) For outpatients, residence (at the time of enrolment) within the defined catchment area around the health facility (see section 7.5.1);
- 5) For outpatients aged ≥ 15 years, absence of symptoms of lower respiratory infection and of diarrhoeal diseases as defined by:
 - a) cough AND ≥ 1 of the following: cough productive of green/yellow sputum, or haemoptysis;
 - b) ≥ 3 loose stools within the previous 24 hours;
- 6) For outpatients aged ≥ 2 months to < 15 years, absence of symptoms of diarrhoeal diseases as defined by: ≥ 3 loose stools within the previous 24 hours;
- 7) Willingness and ability to provide demographic and clinical information, and clinical samples, at the time of enrolment and 28 days later;
- 8) Provision of written informed consent for adult participants; or for children, provision of written consent from a parent/guardian and assent from the child (according to local regulations and practices at each study site).

Controls will be community members in the study site health facilities' catchment areas, frequency matched to participants by age and season (see section 7.5 for details of selection and study activities for community controls).

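### Pathogen-specific incidence multiplies an all-fever incidence by an attributable fraction that, for outpatients, comes from symptom-restricted fevers

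*Protocol*

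**What the plan says.** **The incidence.** Protocol section 7.5.4 says: "The multiplier method requires an estimate of the total number of cases of fever that present to our study sites". Section 7.2.1 provides for that count: "The total number of patients presenting to the hospital with fever each day (or week), including those not in the study" is to be recorded. Section 11.1, secondary objective 1, takes the cases from the defined population, scales them by 1/r and divides by the population size. There r is "the proportion of fevers for which treatment was sought at a study centre". Neither the count nor r is limited by symptoms.

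**The fraction.** The same paragraph ends: "Incidence of fever caused by specific pathogens will be calculated by multiplying the incidence by the AF for that pathogen". Under primary objective 1, section 11.1 says: "For outpatients the attributable fraction (AF) will be calculated for each pathogen or group of pathogens". This is done by site and age stratum, comparing enrolled cases with community controls. A separate AF analysis is planned for inpatients from the controls' area, but it may be dropped if too few come from there.

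**Who can be enrolled.** Section 6 has two symptom criteria, both for outpatients only:
- From age 15: "absence of symptoms of lower respiratory infection and of diarrhoeal diseases as defined by" cough with green or yellow sputum or haemoptysis, and three or more loose stools in 24 hours.
- Under 15: "absence of symptoms of diarrhoeal diseases as defined by" the same stool criterion, with no respiratory criterion.

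**What is logged.** Section 7.2.1 also provides that, for patients screened and excluded, the reason is recorded with age, sex and residence.

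**The concern.** The product of an incidence and a fraction is meaningful only if both refer to the same set of fevers. Here the incidence includes outpatient fevers with diarrhoea and, in those aged 15 and over, with the listed lower respiratory symptoms. The outpatient AF is estimated after those fevers have been removed. Using it for the whole count assumes, without saying so, that each pathogen explains the same fraction of excluded as of eligible fevers. Exclusion by syndrome gives reason to doubt that.

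Outpatients matter most for this calculation, because section 3.2 says that most febrile attenders are not admitted. The results at stake are the disease-burden estimates that secondary objective 1 exists to supply.

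**Working it through.** The protocol states no incidence or AF result, so there is no figure of its own to reproduce. The check compares scope and then uses algebra.

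**Step 1: scope of each term.**

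| Term | Source | Symptom restriction |
|---|---|---|
| Fever count | 7.2.1, 7.5.4, 11.1 | none |
| r | 11.1 | none |
| Outpatient AF | 6, 11.1 | diarrhoea (all ages); listed respiratory symptoms (15 and over) |
| Inpatient AF (conditional) | 6, 11.1 | none |

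The weighting in section 11.1 corrects for the seasonal sampling fraction. It cannot restore syndromes that were never enrolled.

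**Step 2: formula for the outpatient component.** Let I be the all-fever incidence, e the symptom-excluded share of the outpatient fevers to which the AF is applied, AF_R the AF in eligible fevers, AF_E the AF in excluded fevers, and k = AF_E/AF_R.

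- Plan: I x AF_R
- Matching quantity: I x [(1-e) x AF_R + e x AF_E]
- Plan/true = 1/[(1-e) + e x k]

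The ratio equals 1 only if e = 0 or k = 1. The algebra takes r to be the same for eligible and excluded fevers.

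**Step 3: size.** The protocol gives neither e nor k, so both are assumed ranges.

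| e | k=0 | k=0.5 | k=1 | k=2 | k=3 |
|---|---|---|---|---|---|
| 10% | 1.11 | 1.05 | 1.00 | 0.91 | 0.83 |
| 20% | 1.25 | 1.11 | 1.00 | 0.83 | 0.71 |
| 30% | 1.43 | 1.18 | 1.00 | 0.77 | 0.63 |
| 40% | 1.67 | 1.25 | 1.00 | 0.71 | 0.56 |

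For example, at e = 30% and k = 0 the ratio is 1/0.70 = 1.43. At e = 30% and k = 3 it is 1/(0.70 + 0.90) = 0.63.

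**Step 4: an illustration on the scale of cases.** Section 11.2 uses 12% prevalence in cases and 5% in controls.

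- OR = (0.12/0.88)/(0.05/0.95) = 2.59
- AF_R = 0.12 x (1 - 1/2.59) = 0.0737

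This uses the conventional p(1-1/OR). The form printed in section 11.1, p(1-OR), is negative for any OR above 1. That is a separate matter, and the ratios in step 3 do not depend on it.

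Per 100 outpatient fevers the plan attributes 7.37 to the pathogen. With e = 20%, the matching figure is 5.89 if k = 0 and 10.32 if k = 3.

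**Step 5: does restricting the count alone suffice?** Restricting the count to eligible fevers but dividing by an all-fever r gives N_elig/r_all, where N_elig/r_elig is needed. The remaining factor is r_elig/r_all. It equals 1 only if care-seeking is the same for eligible and excluded fevers.

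**The case against.** Several points on the other side stand, and they limit the finding.

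- **Inpatients.** A reader might infer that every AF comes from a symptom-restricted group. The documents do not support that: both symptom criteria apply to outpatients, and an inpatient AF is planned, though conditionally. The ratio above therefore concerns the outpatient component. Its effect on a combined total is diluted by whatever share inpatients contribute with their own AF.
- **Residence.** A reader might infer a further inflation because the catchment is drawn to hold about 80% of outpatients, while the section 7.2.1 count has no stated residence split. But section 11.1 limits the cases to the defined population, and section 7.5.4 limits the survey data to match where a smaller defined population is used. Followed as written, the formula contains no such inflation.
- **Direction by pathogen.** A reader might infer that malaria, arboviral, rickettsial or leptospiral incidence is overstated and respiratory incidence understated. Nothing in the protocol gives k for any pathogen. The respiratory criterion is also narrow: it does not apply under 15 years or to inpatients, and adults whose cough lacks the listed features remain eligible.
- **Strata.** Section 11.1 does not say that one pooled AF will be applied to one total. Applying stratum-specific AFs and summing is compatible with its wording, and the detail could sit in an analysis plan that is not shown.
- **Weight.** This is a secondary objective. The AF, aetiology and resistance analyses for the primary objectives are not affected.

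None of this closes the gap for outpatients. Applying AFs by age and in/outpatient status still leaves an outpatient AF from eligible fevers multiplying an outpatient count that includes ineligible ones.

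**Conclusion.** The concern holds for the outpatient component of secondary objective 1. The count and r cover all fevers, the outpatient AF covers only fevers that pass the symptom criteria, and the protocol neither aligns them nor states an equal-AF assumption. The formula is fixed in the protocol, so this is more than detail left for later.

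The size rests on assumed e and k. For e of 10% to 40%, planned incidence is 1.11 to 1.67 times the true value if the pathogen is absent from excluded fevers, and 0.83 to 0.56 times if its AF there is three times as high. The case k = 0 is an extreme, not an expectation. The mismatch is certain from the text. Its direction and size for any named pathogen are not. It should be corrected before incidence is computed.

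**What to change.** 1. Compute incidence within age group and in/outpatient status, apply that group's AF, and sum.
2. For outpatients, restrict the fever count to eligible fevers, using the exclusion reasons already recorded at screening. Say that the share seen among screened patients is taken to hold for unscreened attenders.
3. Restrict r in the same way by adding symptom questions to the utilisation survey, or state the assumption that care-seeking is the same for eligible and excluded fevers.
4. Label the outpatient result as incidence of fever meeting the study's symptom criteria.
5. Keep the fever tally by age group and in/outpatient status.

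If an all-fever incidence is preferred, state the equal-AF assumption (k = 1) and report a sensitivity range over k, with e estimated from the screening log.

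**Cost.** Changed wording in section 11.1, a few more columns on an existing tally and, if r is restricted, some added survey questions. The price of the restricted version is an incidence for a narrower definition of fever.

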7.6.10 Biomarker assays

In addition to archiving samples at LSHTM for future biomarker investigations, a limited set of assays will be carried out as a part of FIEBRE study activities. These will include the biomarkers in Table 2 that have been identified in previous studies as potentially useful in diagnosing bacterial infection and/or as prognosticators of illness severity. Of note, the identification and investigation of biomarkers of infection is a fast moving field and novel biomarkers likely will be identified by the global scientific community during the time period of this study. Therefore, once FIEBRE samples are available, we will review and revise (if necessary) the list of biomarkers to be tested to prioritize assays that are most likely to lead to public health benefit in fever case management for patient populations typified by FIEBRE participants.

Table 2. Biomarkers identified as potentially useful in distinguishing bacterial from non-bacterial infections, or in predicting illness severity

Biomarker/ test	Supportive evidence from Africa/Asia	Sample requirements and test method
C-reactive protein (CRP)	Variable performance from a multitude of studies, including Asia and to a lesser extent SSA ^{39,40}	10ul EDTA plasma; Luminex assay to be performed at LSHTM
Triggering receptor expressed on myeloid cells (sTREM-1)	Published data ^{39,41,42} ; study of ~2000 febrile children in Uganda (under review, Kain et al)	100ul EDTA plasma; Luminex assays to be performed at LSHTM
Angiopoietin-Tie-2	Some supportive data from Malawi ^{43,44} ; study of ~2000 febrile children in Uganda (under review)	
Interleukin 6 (IL-6)	Study of ~2000 febrile children in Uganda (under review; published data ³⁹	
soluble fms-like tyrosine kinase-1 (sFlt1)	Study of ~2000 febrile children in Uganda (under review)	
Soluble tumor necrosis factor receptor-1 (sTNFR1)	Study of ~2000 febrile children in Uganda (under review)	
Heparin binding protein (HBP)	No data from LMICs. Primarily validated as marker of severity and organ dysfunction ^{39,45,46}	

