In total 250 µl of EDTA plasma will be aliquoted and stored for these assays from all study participants from the day 0 blood draw, including patients and controls. In addition, 250 µl will be aliquoted and stored from each patient’s day 28 blood draw. Comparing biomarker levels on day 0 and day 28 will provide a better understanding of their kinetics, as previous studies suggest that patients in whom some biomarkers fail to normalize could be at higher risk of severe outcome.^{44,47,48}

The biomarker assays will be carried out at LSHTM where patient samples will be archived. The diagnostic and prognostic value of these biomarkers will be assessed to determine their utility alone and in combination in differentiating between bacterial and non-bacterial causes of illness, and in predicting severe outcomes using mortality and severity scores as endpoints.

Biomarker assay results will not be used in clinical management of FIEBRE study participants.

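### Section 11.1 evaluates quantitative biomarkers one at a time and only through cut-dependent measures, which does not deliver the combination and prognostic evaluation set out in section 7.6.10

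*Protocol*

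**What the plan says.** Section 11.1 (secondary objective 3) states: "The sensitivity, specificity, and positive and negative predictive value of each biomarker will be estimated". It adds nothing further for this objective.

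Section 7.6.10 sets the aim more widely. It says "The diagnostic and prognostic value of these biomarkers will be assessed to determine their utility alone and in combination", first for separating bacterial from non-bacterial illness, and then "in predicting severe outcomes using mortality and severity scores as endpoints". It also says "Comparing biomarker levels on day 0 and day 28 will provide a better understanding of their kinetics", so the protocol itself treats the markers as levels.

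Table 2 in the same section lists seven markers or marker groups. Luminex is the only assay method it names ("Luminex assays to be performed at LSHTM"), and it gives no cut for any marker. For heparin binding protein the evidence column reads "No data from LMICs. Primarily validated as marker of severity and organ dysfunction". The list stays open: once samples are available, "we will review and revise (if necessary) the list of biomarkers to be tested".

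Section 11.2 gives no sample size, power or precision for the biomarker objective.

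**The concern.** Sensitivity, specificity and the two predictive values exist only once each concentration has been turned into positive or negative. A marker read on a continuous scale then contributes one bit per patient, and the result depends on where the cut was placed. The unit of analysis in 11.1 is also each biomarker, so an analysis plan that followed it literally would contain no analysis of combinations and none of the mortality and severity endpoints.

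Two things are at stake. A marker with real but moderate discrimination may be estimated too imprecisely to be recognised, chiefly where bacterial cases are few. And where no usable cut exists beforehand, one would have to come from the study data. If it were then scored on the same patients, the marker would look better than it is, and better relative to markers with established cuts.

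**Working it through.** **The two sections side by side**

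| Element of 7.6.10 | Covered by the sentence in 11.1? |
|---|---|
| Each marker, bacterial v non-bacterial | Yes, at an unspecified cut |
| Markers in combination | No analysis stated |
| Prediction of mortality and severity scores | No endpoint or analysis stated |
| Day 0 v day 28 levels | No analysis stated |

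**Inputs for the size**

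The protocol has no biomarker figure to reproduce; its one power statement, in 11.2, concerns infection prevalence in cases and controls.

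- From the protocol: 600 patients per analysis group and 2400 per site (11.2).
- Assumed: the number of bacterial cases. The 5% in 11.2 is for a single infection, and no total bacterial share is given. Taking 5% and 10% as illustrations gives 0.05 × 600 = 30, 0.10 × 600 = 60, and, for one pooled site, 0.05 × 2400 = 120.
- Assumed: log concentrations normal with equal variance, true AUC of 0.60 to 0.70, two-sided 5% level.

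**Formulas**

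The mean shift for a given AUC is d = √2 × Φ⁻¹(AUC). This gives d = 0.358, 0.545 and 0.742 for AUC 0.60, 0.65 and 0.70. The best cut is at d/2, where the Youden index (sensitivity + specificity − 1) is 2Φ(d/2) − 1 = 0.14, 0.22 and 0.29.

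**Information lost by cutting**

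Simulated power of a rank test (equivalent to testing AUC = 0.5) against a two-proportion test at the best fixed cut, with 4,000 to 10,000 replicates per setting:

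| Bacterial / other | AUC 0.60 | AUC 0.65 | AUC 0.70 |
|---|---|---|---|
| 30 / 570 | 46% v 34% | 81% v 65% | 97% v 89% |
| 60 / 540 | 73% v 56% | 97% v 90% | 100% v 99% |
| 120 / 2280 | 96% v 87% | 100% v 100% | 100% v 100% |

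This comparator favours cutting. With a median split and 30 cases, the cut-based figures fall to 28%, 58% and 85%.

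**Overstatement if a cut is chosen and scored on the same data**

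Mean Youden index at the cut that maximises it in the sample, against the best truly achievable value:

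| Bacterial / other | AUC 0.50 | AUC 0.60 | AUC 0.65 | AUC 0.70 |
|---|---|---|---|---|
| 30 / 570 | 0.11 v 0 | 0.23 v 0.14 | 0.29 v 0.22 | 0.36 v 0.29 |
| 120 / 2280 | 0.06 v 0 | 0.18 v 0.14 | 0.25 v 0.22 | 0.32 v 0.29 |

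The excess is about 0.07 to 0.11 with 30 cases and 0.03 to 0.06 with 120. Measured against the true value at the cut actually chosen, it is about 0.09 to 0.11 with 30 cases.

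**Combinations**

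Two independent markers, each with AUC 0.70, have a combined shift of √2 × 0.742. The combined AUC is therefore Φ(√2 × 0.742 / √2) = Φ(0.742) = 0.77. Figures reported separately for each marker would not show this gain.

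**The case against.** The strongest reply is that a protocol may name performance measures in one line and leave cuts, ROC methods and validation to a statistical analysis plan, which is not shown here. With the marker list still open, fixing cuts now could be premature. That stands: the absence of these details is not in itself a fault. What remains is that the one analysis 11.1 does state is narrower than the aim in 7.6.10, and that is a mismatch within the protocol.

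Four stronger readings are tempting, and the document does not support them.

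- A reader might infer that combinations cannot be assessed with these measures. They can: a combined rule or score has a sensitivity and specificity like any single marker. The gap is that 11.1 covers markers singly and gives no method for combining them.
- A reader might infer that untested markers will look too good. No section says cuts will be chosen and scored on the same patients. The entry for heparin binding protein says where evidence is lacking, not that no cut exists. Cuts fixed in advance from outside would not carry this bias.
- A reader might speak of lost power as though a test were planned. The objective is estimation, with no biomarker hypothesis or power stated. Power serves here only as a measure of information.
- A reader might take the 5% in 11.2 as the bacterial share. It refers to one infection, and section 7.6 lists many bacterial targets. Plasma is stored from all participants, so the analysis need not be confined to one group of 600. With more cases the loss shrinks, as the 120-case rows show.

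Sensitivity, specificity and predictive values also answer the case-management question directly, which is a good reason to keep them.

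**Conclusion.** The concern holds as a mismatch between two sections and as a weak choice of sole analysis. Section 11.1 fixes per-marker, cut-dependent measures for quantitative markers, and following it as written would not deliver the combination and prognostic aims of 7.6.10.

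The cost in information ranges from material to negligible. It is about 16 points of proxy power at AUC 0.65 with 30 cases in 600. With 120 cases in 2400 it is about 10 points at AUC 0.60 and essentially nil from 0.65. The overstatement is conditional on cuts being derived and scored on the same patients. All these sizes rest on assumed case numbers, assumed AUCs and an equal-variance normal model; the mismatch itself rests on none of them.

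This is a worthwhile improvement to a secondary objective. It does not threaten the study's primary results.

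**What to change.** Amend the paragraph for secondary objective 3 in section 11.1 so that it matches section 7.6.10:

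- Keep sensitivity, specificity and predictive values. Report them at cuts fixed beforehand from published values or, where none exist, at cuts derived by cross-validation or tested on a held-out site.
- Add the AUC with a 95% confidence interval for each marker on its continuous (log) scale.
- Add a regression model on continuous values, with an internally validated AUC, for marker combinations and for the mortality and severity endpoints named in 7.6.10.

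The change needs no new samples or assays. It costs a few sentences and minor extra analysis, and the validated performance figures will be slightly less favourable than unvalidated ones.
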